1.8 Known and Potential Risks to Human Subjects

Dysport is licensed in the UK for the symptomatic treatment of focal spasticity, spasmotic torticollis, blepharospasm and hemifacial spasm, injected either intramuscularly or subcutaneously targeting the affected muscles or muscle groups, and is also licensed for treatment of severe primary hyperhidrosis of the axillae, injected intradermally.

Side effects of Dysport as experienced with intradermal injection for hyperhidrosis indication were local injection site reactions including pain, bruising, pruritis, and oedema. In addition, rash and compensatory sweating were also reported.

The maximum licensed intradermal dose is 200 U per area of injections. This maximum recommended intradermal dose will not be exceeded in the present study. Additional information regarding risks to human subjects may be found in the SmPC.

Overall, the safety profile of Dysport is well established after more than 20 years of clinical trials and post-marketing experience in various therapeutic and aesthetic indications at various doses with maximum dose used for intradermal indication up to 200 U at single area of injections. In the current proposed study in subjects with chronic scar pain, we believe the risk associated with Dysport use intradermally, to be acceptable, considering the established and known safety profile with intradermal use.

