6.2 Rescue Medication

Paracetamol (acetaminophen), taken orally as required, is the rescue pain medication during the randomised double-blind period (Part B) and will be provided by the CRU to the subject. It can be taken up to four times a day and should not exceed a daily dose of 4000 mg in divided doses. A single dose of rescue medication is defined as 1000 mg (two tablets).

The single paracetamol dose may be lowered to 500 mg (one tablet) if the investigator/subject feels that the dose is higher than what may be required to provide adequate analgesic effect.

For the first week, in Part B post-dose, the investigator may substitute paracetamol with co-codamol (30 mg/500 mg, maximum 4000 mg of paracetamol per day).

If the subject takes the maximum rescue medication dose of 4000 mg paracetamol per day for three consecutive days and still reports uncontrolled scar pain, the investigator should consider discontinuing the subject from the study. If uncontrolled pain elsewhere in the body were to develop, the management of this should be handled on a case-by-case basis.

The rescue medication should be swallowed whole with water and must not be broken or crushed.

The subject will be cautioned on the use of any other medication (over-the-counter or prescription containing paracetamol e.g. Lemsip®).

Rescue medication should not be taken in conjunction with other analgesic medication unless discussed with the investigator.

If rescue medication is taken, an AE and the corresponding rescue medication should be recorded in the eCRF.

The sponsor medical monitor should be contacted if further guidance is required. For questions on concomitant medications prescribed prior to study participation, the sponsor medical monitor should be contacted before the subject is included in the study.

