7.1 Adverse Events

Adverse events will be monitored and reviewed regularly by the sponsor from the time that a subject gives informed consent and throughout the study, and will be elicited by direct, nonleading questioning or by spontaneous reports.

7.1.1 *Definition of an Adverse Event*

An AE is the development of an undesirable medical condition or the deterioration of a preexisting-medical condition, whether or not considered causally related to the product. An undesirable medical condition can be symptoms (e.g. nausea, chest pain), signs (e.g. tachycardia, enlarged liver) or the abnormal results of an investigation (e.g. laboratory findings, ECG).

An AE can include an undesirable medical condition occurring at any time, even if no agent or IMP has been administered.

This definition includes events occurring from the time of the subject giving informed consent until the EoS/ED.

7.1.2 *Adverse Events Categorisation, Recording, and Follow-up*

For all AEs, sufficient information should be obtained by the investigator to determine the causality of the AE (i.e. agent or IMP administration, study procedure or other illness). The investigator is required to assess causality and record that assessment in the eCRF.

Adverse events will be classified by the investigator as mild, moderate or severe according to the following criteria:

- **Mild:** Symptoms do not alter the subject's normal functioning,
- **Moderate:** Symptoms produce some degree of impairment to function, but are not hazardous, uncomfortable or embarrassing to the subject,
- **Severe:** Symptoms definitely hazardous to well-being, significant impairment of function or incapacitation.

The relationship of an AE to agent or IMP administration will be classified by the investigator according to the following:

- **Related:** Reports including good reasons and sufficient information (e.g. plausible time sequence, dose-response relationship, pharmacology) to assume a causal relationship with agent or IMP administration in the sense that it is plausible, conceivable or likely,
- **Not related:** Reports including good reasons and sufficient information (e.g. implausible time sequence and/or attributable to concurrent disease or other drugs) to rule out a causal relationship with agent or IMP administration.

7.1.2.1 *Assessment of Expectedness*

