11.3.1.2 Randomised Double-blind Period (Part B)

Descriptive statistics will be calculated on the safety parameters. No formal statistical tests of safety parameters are planned.

All AEs will be coded according to the latest version of the Medical Dictionary for Regulatory Activities (MedDRA).

Treatment emergent AEs (TEAE) summaries will include the overall incidence (by system organ class and preferred term), events by maximum intensity, events by relationship to study drug, events leading to discontinuation of study drug, and SAEs.

Physical examination findings, vital signs, ECG recordings and clinical laboratory parameters will be summarised descriptively at each timepoint. Actual and change from baseline data will be calculated and summarised where data are available. The investigator's interpretation of 12-lead ECGs will be listed.

Concomitant medications will be coded by using the latest version of the World Health Organisation (WHO) drug dictionary and will be summarised with the number and percentage of subjects receiving concomitant medication by drug class and preferred drug name.

Demographic variables (age, height, weight and body mass index) and medical and surgical history will be summarised.

11.3.2 *Pharmacokinetic Evaluation*

Not applicable.

11.3.3 *Pharmacodynamic/ Efficacy Evaluation*

11.3.3.1 *Pre-Randomisation Run-in Period*

Only listing on NRS data will be provided.

11.3.3.2 *Randomised Double-blind Period*

Analysis of the primary endpoints

Four endpoints have been defined to meet the study primary objective. They are presented in [Table 3](#) with their associated estimate and estimand.

Table 3 Primary Objective - Analysis of Primary Endpoints

Objective	Assessments	Endpoints	Estimate of treatment effect	Estimand
To describe the pharmacodynamic analgesic profile of intradermal doses of Dysport in subjects with abdominal or thoracic chronic scar pain.	Worst pain and average pain within the last 12 hours as assessed by the spontaneous NRS score.	Time to onset, i.e. time to decrease from baseline of two points in the spontaneous NRS score.	The number (%) of subjects who reach the time to onset in each treatment group. The mean time to onset in each treatment group.	For each estimate, the associated estimand will be based on "treatment policy" strategy (i.e. regardless of the intake of rescue medication).

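### The moderate AE grade bars uncomfortable or embarrassing events, so an uncomfortable event with some functional impairment fits none of the three grades

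*Protocol*

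**What the plan says.** Protocol 7.1.2 sets a closed three-grade scale: "Adverse events will be classified by the investigator as mild, moderate or severe according to the following criteria". The three grades are worded as follows:

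- The lowest grade, mild, rests on function alone: "Symptoms do not alter the subject's normal functioning".
- The middle grade, moderate, pairs a degree of impairment with three exclusions: "Symptoms produce some degree of impairment to function, but are not hazardous, uncomfortable or embarrassing to the subject".
- The top grade, severe, can be reached by any one of three routes: "Symptoms definitely hazardous to well-being, significant impairment of function or incapacitation".

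The SAP has no severity scale of its own. SAP 5.8.3 leaves a missing grade as missing and takes the worst grade when an event recurs in a subject. It has no rule for an event that satisfies none of the criteria.

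The grade is used in three places. Protocol 11.3.1.2 includes "events by maximum intensity" among the TEAE summaries. The overview table in SAP 5.8.3 counts subjects with at least one severe TEAE. The TEAE definition in SAP 5.8.3 also takes in events whose severity worsens after dosing. SAP 5.8.3 has a counting rule for severity summaries but lists no table by intensity, and SAP 2.6, which records departures from the protocol, does not say that this table was dropped.

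Two sources of uncomfortable events are built into the study. Protocol 1.8 gives the known effects of intradermal Dysport as "local injection site reactions including pain, bruising, pruritis, and oedema", together with rash and compensatory sweating. Protocol 6.2 adds pain events: "If rescue medication is taken, an AE and the corresponding rescue medication should be recorded in the eCRF".

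**The concern.** In the moderate criterion the negation governs all three adjectives, so an event that is uncomfortable or embarrassing cannot be moderate. If it also limits function to some degree, it cannot be mild. If it is not definitely hazardous and the impairment is not significant, it cannot be severe. An injection-site reaction or a pain event that limits the subject a little is a realistic example.

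The grades are also not monotone. Discomfort is compatible with mild, is excluded from moderate, and plays no part in severe.

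Safety and tolerability across doses is a secondary objective, and intensity is one of the ways in which the protocol proposes to describe it. If the written criteria do not yield a grade, what is recorded depends on how the assessor departs from them.

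**Working it through.** The plan states no figure on this point. The check is to cross the attributes named in the three criteria and see which grade each combination meets.

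**Inputs (Protocol 7.1.2).** Impairment: none, some, significant (incapacitation is taken with significant, and some is taken to mean less than significant). Discomfort or embarrassment: no, yes. Hazard: not hazardous, definitely hazardous. That gives 3 × 2 × 2 = 12 combinations.

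| Impairment | Discomfort or embarrassment | Not hazardous | Definitely hazardous |
|---|---|---|---|
| none | no | mild | mild and severe |
| none | yes | mild | mild and severe |
| some | no | moderate | severe |
| some | yes | **no grade** | severe |
| significant | no | severe | severe |
| significant | yes | severe | severe |

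One combination has no grade, two have two grades, and 12 − 1 − 2 = 9 have exactly one.

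**Possible hazard.** Moderate requires an event that is not hazardous, while severe requires definite hazard. If possible hazard is added as a third level, there are 3 × 2 × 3 = 18 combinations. Suppose that a possibly hazardous event fails the moderate criterion. Then the two new rows with some impairment have no grade, and the gaps become 1 + 2 = 3 of 18. This step rests on that supposition; the gap in the table does not.

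**Does a dropped word explain it?** The sentence may have been meant to say that moderate events are not hazardous *but* are uncomfortable or embarrassing. That is an inference; the documents do not say so. If discomfort then became a requirement for moderate, the gap would move to some impairment without discomfort and would still be 1 of 12. The corrected text therefore has to permit discomfort, not require it.

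**Which outputs are affected.**

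- Maximum-intensity summary (Protocol 11.3.1.2): any inconsistent grade can shift a subject between categories.
- Severe-TEAE row (SAP 5.8.3): only an upgrade to severe changes it. Grading an event mild or moderate leaves it as it is.
- Worsening limb of the TEAE definition (SAP 5.8.3): only events that began before dosing. Reactions to the Part B injection start after dosing and are TEAEs by start date, whatever their grade.

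**Size.** The overview table counts subjects, not events. With six subjects per arm (Protocol synopsis), one subject moved into the severe row changes that arm by 1/6 = 16.7 percentage points. In the column for all Dysport it is 1/(3 × 6) = 1/18 = 5.6 points. A second upgraded event in the same subject, or one in a subject who already has a severe TEAE, adds nothing.

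**After the correction below.** Let moderate permit discomfort and exclude only definite hazard, and let the highest grade met apply. Of the 18 combinations, severe takes the 6 that are definitely hazardous plus the 4 others with significant impairment, which is 10. Moderate takes the 4 with some impairment and no definite hazard. Mild takes the 4 with no impairment and no definite hazard. 10 + 4 + 4 = 18, each with exactly one grade.

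**The case against.** The best reply is that the three grades share an obvious functional axis: function unaltered, somewhat impaired, significantly impaired. An experienced investigator will place a partly limiting event on moderate and pass over the stray adjectives. Mild would contradict the finding that function is altered, and severe would assert a hazard or a significant impairment that is not there. This stands, and it is why moderate is the likely grade in practice. It does not repair the text, because that grade still departs from the written criterion and nothing ensures that the departure is uniform.

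Several limits on the consequences also stand:

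- Protocol 1.8 lists the local reactions without frequencies, and no section says that they limit function. A sore or itchy site that leaves function unaltered is validly mild. The affected subset may be small or empty.
- There is one site, the assessing staff are blinded (Protocol 3.4.2), and the same assessor is to be kept where possible (Protocol 7). Inconsistent grading should not systematically favour an arm.
- Safety analysis is descriptive, and all AEs are listed individually.

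A reader might infer that affected events must end up as mild or severe, or that tolerability by intensity cannot be interpreted across doses. The documents do not support either reading, for the reasons above.

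**Conclusion.** The wording is wrong as it stands and should be corrected. An uncomfortable or embarrassing event with some functional impairment, no significant impairment and no definite hazard meets no grade, and the scale is out of order on discomfort. Neither document offers another definition that would resolve it.

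The consequence is possible inconsistency in intensity grades. It reaches the maximum-intensity summary and, only where a subject is upgraded, the severe-TEAE row. The figure of 16.7 points is the weight of one subject in an arm of six. It should not be read as a weight per event or as an estimate of expected error, because the number of affected subjects is not known. It assumes six subjects in the arm's safety population; replacements would make that number larger and the weight smaller.

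A reader might also infer that the TEAE classification of injection-site reactions is compromised. It is not, since those starting after dosing qualify by start date. AE capture, causality, seriousness and the efficacy endpoints do not depend on the grade.

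**What to change.** Reword the moderate criterion in Protocol 7.1.2 along these lines: *some impairment of function, which may be accompanied by discomfort or embarrassment, without definite hazard to well-being*. Add one sentence stating that the highest grade met applies. Both parts are needed. Excluding only definite hazard gives possibly hazardous events with some impairment a grade. The highest-grade rule settles definitely hazardous events with unaltered function, which now meet both mild and severe. The mild and severe criteria can stay as they are.

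Then:

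1. Send the corrected definition to the site.
2. Have the investigator re-check, while blinded and before database lock, the grades of recorded AEs that combine discomfort or embarrassment with some impairment. The blind data review in SAP 5.3 is a natural deadline.
3. List in SAP 5.8.3 the TEAE table by maximum intensity that Protocol 11.3.1.2 promises.

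The cost is a short protocol change, a site note, a small blinded re-check and one table already promised.

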7.1.4 Suspected Unexpected Serious Adverse Reactions

Suspected unexpected serious adverse reactions (SUSARs) are serious events that are not listed in the latest approved Dysport IB or the lidocaine SmPC in the UK and that the investigator identifies as related to agent or IMP or procedure.

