5.8 Safety

5.8.1 *General Consideration*

All safety summaries and analyses will be based upon the Safety population. All safety data will be included in subject data listings (see listing detail conventions in Appendix A5). There will be no statistical comparison between the treatment groups for safety data.

If conversion factors are used, they should be presented either in the relevant section or a link to section 7 should be added.

5.8.2 *Extent of exposure*

In Part B, duration of exposure will be defined in weeks as:
([date of last visit attended – first IMP injection date] +1)/7.

The total dose received will be derived as followed:

- Total Dose (in U) = Number of injection site*Number of units of Dysport received,
- Total dose (in U/cm²) = Total dose / (Total painful area at day 1 pre-dose).

The following extent of exposure summaries will be presented for Part B, by treatment group and all Dysport:

- Summary of the number of injections sites,
- Summary of the volume injected (total and per site),
- Summary of the total dose received by treatment group,
- Summary of the total dose in U/cm² received by treatment group.

The following extent of exposure listings will be presented for Part A and Part B:

- Listing of exposure data (Part B only),
- Listing of subjects receiving test drugs from different batches.

5.8.3 *Adverse Events*

All adverse events (AEs) recorded in the eCRF will be coded using the latest version of MedDRA dictionary in effect within IPSEN at the time of the database lock. AEs will be classified as treatment-emergent AEs (TEAEs) according to the rules below:

- Events with start date and time on or after the date and time of IMP administration in Part B and up to End of Study (EoS) visit or Early Discontinuation (ED).
- Events whose severity worsens on or after the date and time of IMP administration in Part B and up to EoS visit or ED visit,
- Refer to appendix [A3](#) for handling of partial date. In the case where it is not possible to define an AE as treatment emergent or not, the AE will be classified by the worst case; i.e. treatment emergent.

The following summary will be provided by total dose and treatment group (i.e. by injection site dose) and all Dysport for Part B:

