- An overview table summarizing the number and percentage of subjects with at least one of the following AEs: any AE; any TEAE; any severe TEAE; treatment-related TEAE; TEAE leading to discontinuation from the study, Serious TEAE, treatment-related Serious TEAE, Serious TEAE leading to death, treatment-related Serious TEAE leading to death, Serious TEAE leading to discontinuation from the study, any Adverse Events of Special Interest (AESI).
The ranges to use for the dose will be precisely defined during the data review meeting.

The following summaries will be provided for Part B by treatment group and all Dysport groups:

- A summary of the number and percentage of subjects reporting a TEAE by treatment group, SOC and PT,
- A summary of the number and percentage of subjects reporting a TEAE by treatment group and PT,
- A summary of the number and percentage of subjects reporting a TEAE by treatment group, causality, SOC and PT,
- A summary of non-serious TEAE by treatment group, SOC and PT.

AEs summaries will be ordered in term of decreasing frequency for SOC and PT within SOC in the treatment group (Part B) and then similarly by decreasing frequency in the treatment group, and then alphabetically for SOC and PT within SOC.

AEs will be counted as follows:

- Subjects with more than one AE within a particular SOC are counted only once for that SOC. Similarly, subjects with more than one AE coding to a particular PT are counted only once for that PT;
- Subjects reporting a TEAE more than once within that SOC/ PT, the TEAE with the worst-case severity will be used in the corresponding severity summaries;

- Subjects reporting a TEAE more than once within that SOC/ PT, the TEAE with the worst-case relationship to study medication will be used in the corresponding relationship summaries;
- If the severity is missing for a TEAE, it will be considered as missing in the summary tables;
- If the causality is missing for a TEAE, it will be considered missing in the summary tables;
- The non-serious TEAEs table should include a specific row “any non-serious TEAE above x%”.

In addition, for each part, a listing with all AEs data will be listed by treatment group including non-TEAEs, Treatment-emergence status will be flagged in the listing, and AESI will also be flagged.

Deaths, Serious Adverse Events, and Other Significant Adverse Events

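### A TEAE whose causality is still missing is left out of the treatment-related rows, and the protocol gives no default for an event with too little information to classify

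*Protocol*

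**What the plan says.** **Protocol 7.1.2.** Causality has two categories.

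- Related applies to reports with "good reasons and sufficient information (e.g. plausible time sequence, dose-response relationship, pharmacology) to assume a causal relationship". The sentence then sets a low threshold: a link that is only conceivable is enough.
- Not related applies to reports with "good reasons and sufficient information (e.g. implausible time sequence and/or attributable to concurrent disease or other drugs) to rule out a causal relationship".

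There is no not-assessable category and no default. The same section puts two duties on the investigator: "For all AEs, sufficient information should be obtained by the investigator to determine the causality of the AE", and "The investigator is required to assess causality and record that assessment in the eCRF".

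**SAP 5.8.3.** The rule for a blank is: "If the causality is missing for a TEAE, it will be considered missing in the summary tables". The overview table has rows for treatment-related TEAEs and treatment-related serious TEAEs, and a further table gives TEAEs by causality. Where it cannot be determined whether an event is treatment-emergent, "the AE will be classified by the worst case".

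**SAP 5.1.2.** A missing category is displayed when one occurs. Unless otherwise specified, subjects with missing data are left out of percentages.

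**The concern.** There are two separate points.

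The first is wording. Both categories ask for sufficient information, so the definitions do not say where to put an event that lacks it. Such events can be foreseen here. After Day 1 the next scheduled clinic visit is Week 6, and adverse events in between are collected by telephone (Protocol 5.2.3.2). Each use of rescue medication also generates an adverse event, recorded from a home diary (Protocol 6.2 and 10.2). A rise in scar pain after injection into that scar could reflect the injection or the underlying condition.

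The second is counting. A TEAE with blank causality is not imputed as related, so it does not enter the treatment-related rows. Those rows are the main causal summary for the secondary objective on safety and tolerability. In arms of six, a single subject is visible in the percentage.

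**Working it through.** **1. Do the definitions cover every event?**

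| State of the report | Related | Not related |
|---|---|---|
| Enough information, link at least conceivable | Met | Not met |
| Enough information, link ruled out | Not met | Met |
| Not enough information | Not met as worded | Not met as worded |

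The third row has no stated home. It should be rare: timing is among the listed examples of information supporting a link, and a subject reporting by telephone will normally give it.

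**2. Does the wording gap lead to a blank field?** Not by itself. Recording an assessment is mandatory, so the investigator facing a third-row event should still choose a category, without guidance on which. The SAP rule applies only if the field is empty and stays empty after queries.

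**3. How does the SAP resolve other doubts about safety data?**

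| Uncertain item | SAP section | Handling |
|---|---|---|
| Treatment emergence | 5.8.3 | Worst case: emergent |
| Whether the subject was treated | 4.4 | Assumed treated |
| Missing or partial AE onset date | A3 | Conservative: on treatment unless dates show otherwise |
| Relationship, repeated events in one SOC/PT | 5.8.3 | Worst recorded value |
| Missing severity | 5.8.3 | Left missing |
| Missing causality | 5.8.3 | Left missing |

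The repeated-event rule selects among recorded values and does not fill a blank.

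**4. Weight of one subject.** The plan states no figure to reproduce. Inputs: six subjects per Dysport dose (Protocol 11.2; SAP 2.3 gives four groups of six), hence 3 × 6 = 18 on Dysport. Take one subject whose only possibly related TEAE has missing causality, and let k be the number of other subjects in the arm with a related TEAE.

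*Denominator kept at six.* Shortfall against counting the subject as related: (k+1)/6 − k/6 = 1/6 = 16.7 points. For all Dysport: 1/18 = 5.6 points.

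*Subject removed from the denominator (SAP 5.1.2).* Shortfall: (k+1)/6 − k/5 = (5k + 5 − 6k)/30 = (5 − k)/30.

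| k | Shortfall |
|---|---|
| 0 | 5/30 = 16.7 points |
| 2 | 3/30 = 10.0 points |
| 5 | 0 |

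So 16.7 points is the maximum per subject for one arm. If the event was in truth unrelated, removing the subject gives k/5 instead of k/6, which overstates the percentage whenever k is at least 1. The count of related subjects can only be lowered; the percentage depends on the denominator, which SAP 5.8.3 does not fix for this case.

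**The case against.** The case for leaving the plan alone is substantial.

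- **The threshold for Related is low.** Most events that cannot be ruled out will be conceivable, hence Related. This stands, and makes the wording gap narrow.
- **Blanks should be few.** Causality must be recorded. Missing data are queried for the whole database (Protocol 12.3), and reasons for missing items are required (15.3.2). Unscheduled visits are possible (5.1), and continuing events are reviewed at each later assessment (7.1.2.2). This also stands. A reader might infer that poorly documented events will routinely end up missing; the documents do not support that.
- **The SAP does not contradict itself.** A reader might see a conflict with the worst-case rule for treatment emergence. But that is a derived status, whereas causality is a medical assessment, and missing severity is left missing in the same way. It is a difference in approach.
- **Nothing is hidden.** The event stays in the overall TEAE counts and the AE listing, and a missing category can be shown. Displaying missing openly is a defensible convention in a descriptive study of about 24 subjects.
- **Serious events are largely protected.** The SUSAR definition covers events "that the investigator identifies as related to agent or IMP or procedure", so a reader might infer that a blank lets a serious event escape. Protocol 7.1.3 requires every SAE to be reported within 24 hours whatever the suspected relationship, lists causality in the minimum information, and has the sponsor ask for it when absent.

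What remains is that the definitions state no default and that the SAP's rule for any residual blank works in one direction on the related count.

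**Conclusion.** The point holds in limited form. Protocol 7.1.2 lacks a default for an event with insufficient information. Independently, SAP 5.8.3 leaves any causality still missing after queries out of the treatment-related rows. This can only lower the related count, and it is less conservative than the SAP's treatment of three other safety uncertainties.

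The effect is at most 16.7 percentage points per affected subject in an arm of six, and 5.6 points for all Dysport with the denominator held at 18. The arm figure applies in full if the denominator stays at six or if no other subject in the arm has a related event; otherwise it is smaller. It assumes that the subject has no other related TEAE. The documents do not say how many causality values will be missing, and the safeguards suggest few, so no total understatement per arm can be given. Nor can a bias in favour of Dysport be claimed, because blanks may occur on placebo too.

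This is a cheap improvement to the safety summary rather than a flaw that threatens the study's conclusions.

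**What to change.** **SAP 5.8.3.** Replace the missing-causality rule with: a TEAE whose causality is still missing at database lock is counted as related in the overview and causality tables; the subject stays in the denominator; a footnote gives the number so counted in each treatment group.

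**Protocol 7.1.2.** Add one sentence: an adverse event for which a causal relationship cannot be ruled out is recorded as Related. This makes the two categories exhaustive.

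**Cost.** One sentence or short rule in each document, and no new data. Related counts may be slightly higher, and some counted events may in truth be unrelated; the footnote lets the reader see how many rest on the rule.
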